6.2. Secondary outcomes

6.2.1. Acute GVHD: Occurrence of grade II, III and/or IV skin, gastrointestinal or liver abnormalities fulfilling the IBMTR criteria for acute GVHD.

6.2.2. Chronic GVHD: Occurrence of symptoms in any organ system fulfilling the criteria of chronic GVHD.

6.2.3. Relapse: disease recurrence or persistent disease for patients not in CR at transplant. Those who survive without recurrence or persistent disease are censored at the date of last contact.

6.2.4. Progression: increase in marrow blasts to $> 20\%$; patients without progression are censored at time of most recent marrow examination.

6.2.5. Disease-free survival: survival without death or relapse. Those who survive without recurrent or persistent disease are censored at the date of last

contact.

6.2.6. Progression-free survival: survival without increase in marrow blasts to >20%; patients without progression are censored at time of most recent marrow examination.

6.2.7. Overall survival: Surviving patients are censored at the date of last contact.

7.0 DATA COLLECTION:

All data necessary for this study will be collected using the existing mechanisms of the CIBMTR under, operating under the “NMDP and CIBMTR Protocol for a Research Database for Hematopoietic Stem cell Transplantation and marrow Toxic Injuries”, version 6.0, (NCT01166009) (Appendix A). The Informed Consent for this protocol is also found in Appendix A. These data collection mechanisms support the reporting required for the Stem Cell Therapeutic Outcomes Database (SCTOD), and the research endeavors of the CIBMTR. Existing data instruments and procedure manuals can be found at www.cibmtr.org/DataManagement. Registration of patients and submission of data will follow standard CIBMTR procedures.

8.0 STUDY DESIGN:

This study initially had a target accrual of 240 patients older than age 65 for the 100 day mortality primary endpoint. Sample sizes were based on an inferiority test of the hypothesis that the 100 day mortality rate in the ≥ 65 year old cohort is higher than 20%, the approximate 100-day mortality rate in a 55-64 year old cohort¹². The study was designed to have approximately 80% power to detect a 6.5 % or greater increase in 100 day mortality rate in the ≥ 65 year old cohort. Table 1 below shows the power of the test for various 100 day mortality rates.

Table 1.	
True 100 day mortality rates	Power
0.21	10%
0.22	20%
0.23	32%
0.24	46%
0.25	60%
0.26	73%
0.27	83%
0.28	90%
0.29	94%

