Based on an 80% power with an assumption of a 25% 100 day mortality in the most favorable group and a delta as indicated, the number of patients needed for each of the analyses is listed below in Table 2. The anticipated accrual for Part I was based on power calculations for a primary outcome of 100 day survival after HCT in patients 55-64 compared to 65 and older. Based upon the distribution of age (65-69 vs. 70 and over), performance score, HCT Comorbidity index¹⁴, IPSS score, and disease status in the first 180 patients enrolled, we anticipate that 700 patients will be required to complete an analysis of prognostic factors for early outcome in patients 65 and older.

Table 2: Number of patients required to test differences in 100 day mortality with 80% power for specified prognostic factors

Prognostic Factor	Number of Patients based on expected difference		
	delta =0.1	delta =0.15	delta =0.2
Age			
<70	580	246	130
≥70	183	78	41
Total	763	324	171
HCT-CI (Sorrer, et al)			
0-2	294	118	59
≥3	222	89	45
Total	516	207	104
Secondary MDS			
No	649	265	133
Yes	163	67	34
Total	812	332	167
Cytogenetics			
Good/Intermediate	376	152	76
Poor	194	79	40
Estimated Unknown/missing/not done	78	32	16
Total	648	263	132
IPSS			
Low.int-1	311	125	62
Intermediate-2/high	214	87	43
Evaluable patients	525	202	105

The above sample size calculations for prognostic factors are based on the estimated frequencies of these potential risk factors using the data accrued in the first 180 patients and a binary response of alive or dead at 100 days. The final analysis of these factors will be performed in a logistic regression model for 100 day survival or a Cox regression model for other events in the cohort of patients age 65 and older.

The distribution of relevant prognostic factors shown in sections 3.2 and 3.3, and in the power calculations shown in Table 2 will be reviewed after accrual of 500 patients age 65 and over. Adjustments will be made to the final accrual projections at that time.

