8.1. Variables to be analyzed for their association with primary and secondary outcomes

8.1.1. Patient related:

- Age: in five year increments (or appropriate cutpoint based on data analysis)
- Gender: male vs. female
- Race: Caucasian vs non-Caucasian
- Karnofsky performance status: <80% vs. ≥80%
- Sorror co-morbidity Index

8.1.2. Disease related:

- WHO Disease classification at diagnosis and just prior to HCT
- FAB classification
- Pretransplant WBC and untransfused platelet count and hemoglobin concentration
- IPSS score immediately prior to transplantation
- WPSS score immediately prior to transplantation
- Cytogenetics
- Primary versus secondary MDS
- Time from diagnosis to transplant: <1 year vs. ≥ 1 year (or more appropriate cutpoint based on data analysis)
- Agents used for prior therapy

8.1.3. Transplant related:

- Conditioning regimen: more versus less intensive; specific regimens to be evaluated if numbers of patients sufficient
- Donor age
- Donor-recipient CMV status: -/- vs. -/+ vs. +/- vs. +/+
- Donor-recipient HLA match: HLA matched sibling vs. 8/8 locus (HLA- A, B, C, DRB1) matched unrelated donor vs. 7/8 locus matched unrelated donor
- Stem cell source: bone marrow vs. peripheral blood
- GVHD prophylaxis: Cyclosporine or Tacrolimus + Methotrexate vs. ex vivo T- cell depletion vs. other
- Donor-recipient gender match: male-male vs. male-female vs. female-male vs. female-female
- Transplant center characteristics: transplant volume, years of operation, academic affiliation

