4.1. Collection of Recipient Data

Recipient data are collected from pre-existing data within the recipient's medical record chart at the transplant center. Transplant Centers complete the forms at the following time-points.

Time-point	Data Collected
At registration	Name Social Security Number (U.S. participants only) Mother's maiden name City State Country of birth
At the time of transplant	Demographic data such as race and ethnicity, gender, birth date, Median household income (U.S. participants only), Education (U.S. participants only), occupation HLA typing data Pre-transplant disease-specific data such as blood counts, disease status, cytogenetics Co-existing disease at the time of transplant

	Functional status Organ function prior to transplant History of infection exposure prior to transplant Conditioning regimen HSC product manipulation
100 days, six months, one year, two year, post-transplant	Engraftment – neutrophil and platelet recovery Acute and chronic GVHD Chimerism Organ function New malignancy Disease Status Functional status Ability to return to work or school Second transplant Donor leukocyte infusion
Annually starting year three	Acute and chronic GVHD New malignancy Disease Status Functional status Ability to return to work or school Second transplant
At time of death	Primary and contributing cause of death

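### Disease status at transplant is cited for the 700-patient target and enters the relapse definition, but it is in no covariate list, so the age comparison on relapse and disease-free survival may be confounded by remission status

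*Protocol*

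**What the plan says.** The protocol mentions disease status in four relevant ways.

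- **Sample size.** Section 8.0 (prognostic factors) lists the factors whose distribution led to the larger accrual, ending with "IPSS score, and disease status in the first 180 patients enrolled". It concludes: "we anticipate that 700 patients will be required to complete an analysis of prognostic factors for early outcome in patients 65 and older".
- **Data collection.** The Research Database protocol in Appendix A, Section 4.1, has centers report at the time of transplant "Pre-transplant disease-specific data such as blood counts, disease status, cytogenetics".
- **Event definition.** Section 6.2.3 reads "Relapse: disease recurrence or persistent disease for patients not in CR at transplant". Section 6.2.5 builds DFS from death or relapse and so inherits that definition.
- **Covariates.** Section 8.0 says the models will examine the variables of Section 3.0, chosen by forward stepwise selection, and that a 55-64 cohort from the same centers is included. Section 8.1 gives the detailed list of variables to be analyzed. Its disease-related part includes "IPSS score immediately prior to transplantation", WPSS, WHO class, blood counts, cytogenetics and earlier agents. Neither Section 3.2 nor Section 8.1.2 names disease status or remission at transplant.

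**The concern.** A patient transplanted outside CR can have a relapse event through persistent disease. A patient transplanted in CR can have one only through recurrence. Remission status at baseline therefore helps decide what counts as an event, quite apart from any prognostic value it has.

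Aim 3.1 compares relapse and DFS between Medicare beneficiaries and patients aged 55-64. Nothing is randomized, and Section 5.0 leaves eligibility for transplant to local practice, so the proportion in CR may differ between the age groups. If it does, the models as listed would attribute part of a remission difference to age. Section 9.1 describes MDS-free survival as central to the study's purpose, so the DFS comparison will be read closely.

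There is also a plain inconsistency. A factor said to justify 700 patients is neither powered in Table 2 nor listed for the models. The review after 500 patients is tied to Sections 3.2 and 3.3 and Table 2, so it does not cover this factor by name either.

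**Working it through.** **Step 1. Trace the five factors named for the 700 target.**

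| Factor named in 8.0 | Section 3.2 | Section 8.1 | Table 2 row |
|---|---|---|---|
| Age | yes | yes | yes |
| Performance score | yes | yes | no |
| HCT comorbidity index | yes | yes | yes |
| IPSS | yes | yes | yes |
| Disease status | no | no | no |

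Disease status is the only one absent from all three places. Section 3.3 (transplant characteristics) does not contain it either.

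**Step 2. Try to reproduce the plan's figure.** The stated inputs are "Based on an 80% power with an assumption of a 25% 100 day mortality in the most favorable group and a delta as indicated", with "a binary response of alive or dead at 100 days" as the outcome. With p1 = 0.25, p2 = 0.25 + delta, r = n2/n1 from each row's own split and p̄ = (p1 + r·p2)/(1 + r):

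n1 = [z_α √((1 + 1/r) p̄(1 − p̄)) + z_β √(p1(1 − p1) + p2(1 − p2)/r)]² / delta², and total N = n1(1 + r).

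The protocol states no alpha for Table 2. One-sided 0.05 (z_α = 1.645, z_β = 0.842) is an assumption. At delta = 0.10:

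| Row | Stated | Recomputed |
|---|---|---|
| HCT-CI | 516 | 527 |
| Secondary MDS | 812 | 790 |
| Cytogenetics, evaluable (376 + 194) | 570 | 570 |
| IPSS | 525 | 534 |
| Age | 763 | 698 (752 with continuity correction) |

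Four rows agree within 3%; age agrees only with a continuity correction. Two-sided 0.05 from a 25% baseline reproduces no row, and most of the delta 0.15 and 0.20 entries do not reproduce from that baseline. The target of 700 equals none of the stated totals (763, 516, 812, 648, 525). No disease-status calculation exists to check.

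**Step 3. What a disease-status row would need.** The protocol gives no split, so the share in the smaller status group is assumed. Delta is 0.10, with the other inputs as above.

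| Smaller share | N, one-sided | N, two-sided | Power at 700, one-sided | Power at 700, two-sided |
|---|---|---|---|---|
| 10% | 1393 | 1758 | 56% | 45% |
| 20% | 792 | 1000 | 76% | 66% |
| 30% | 609 | 770 | 85% | 76% |
| 40% | 537 | 681 | 88% | 81% |
| 50% | 518 | 658 | 89% | 82% |

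Whether 700 is enough for this factor depends on a split that is not reported.

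**Step 4. Illustrate the possible shift in the age contrast.** With no true age effect and no adjustment:

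shift = (difference in CR share) × (difference in event rate between not-CR and CR).

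All rates here are assumed: 20% of one group and 40% of the other in CR, and relapse of 20% in CR.

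- Relapse 30% if not in CR: 0.2 × 0.20 + 0.8 × 0.30 = 28%, against 0.4 × 0.20 + 0.6 × 0.30 = 26%. The shift is 2 points; ln(0.72)/ln(0.74) gives a hazard ratio of about 1.09.
- Relapse 50% if not in CR: 0.04 + 0.40 = 44%, against 0.08 + 0.30 = 38%. The shift is 6 points; ln(0.56)/ln(0.62) gives about 1.21.
- Equal CR shares: the shift is zero whatever the relapse rates.

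**The case against.** **The 700 target concerns 100-day mortality.** This stands. Table 2 uses that endpoint, which is primary and does not depend on CR. The sample-size sentence shows that disease status was regarded as a relevant factor; it says nothing about bias in relapse or DFS. That argument rests on Section 6.2.3 alone.

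**Disease status is not defined in Section 8.0.** Also true. The sentence and Table 2 differ elsewhere (performance score has no row; secondary MDS and cytogenetics have rows but are not named in the sentence), so the term may have been used loosely. If so, the wording still needs reconciling. The relapse definition raises the confounding question under either reading.

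**The lists could be extended.** Section 3.2 introduces its items with *including*, no sentence forbids further covariates, and a statistical analysis plan may add some. This softens the point, but Section 8.1 is written as the list of variables to be analyzed, and it disagrees with the protocol's own rationale.

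**Existing covariates cover part of the ground.** Pre-transplant IPSS, WPSS, WHO class, blood counts, cytogenetics and prior agents would absorb some of any imbalance. None of them is defined as CR versus not in CR.

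**Remission is partly a result of prior therapy.** This stands. A reader might infer that prior-therapy effects are also confounded and that remission should be forced into every model. Conditioning on it could instead remove part of the effect that Section 3.2 sets out to evaluate.

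**Progression-free survival.** A reader might extend the argument to it. Section 6.2.6 uses marrow blasts above 20% whatever the status at transplant, so the reasoning does not carry over.

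**Conclusion.** The point holds for relapse and DFS in the age comparison. Disease status is cited for the target and collected before transplant, and remission status is built into the relapse event, but disease status is missing from Sections 3.2 and 8.1.2 and from Table 2. The comparison may be confounded by remission status.

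The direction and size are unknown. The documents give neither CR shares by age group nor event rates by CR status. The 2 to 6 points above illustrate assumed rates without adjustment; they are not an estimate, and partial proxies would reduce them. A reader might infer that the age comparison is biased, or that 700 patients are too few. The documents support neither: the bias vanishes with equal CR shares, and the adequacy of 700 for this factor cannot be judged without its split. The primary 100-day mortality analysis is not affected through the relapse definition. This should be corrected, but it does not undermine the study.

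**What to change.** 1. Add disease status at transplant (CR versus not in CR) to Sections 3.2 and 8.1.2.
2. In the relapse and DFS models for the comparison of patients 65 and older with those aged 55-64, keep it in the model or stratify on it, so that forward stepwise selection cannot drop it. Stratification lets the two status groups have separate baseline hazards, which suits an event that arises differently in each, although it does not make the events identical.
3. Report prior-therapy effects with and without it, since it may be a mediator.
4. Add a disease-status row to Table 2 from the observed split, or remove the factor from the rationale for 700.
5. Do not require it for progression-free survival on this argument.

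The cost is one more covariate. Completeness in the 55-64 cohort must be confirmed first: Section 9.5 says comprehensive forms cover only a subset of registered patients, although case selection can be modified for a specific study.

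### Table 2 sizes Age by one formula and the other four factors by another, at mortality rates that contradict the stated assumption, so its single 80% power claim does not hold across rows

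*Protocol*

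**What the plan says.** Protocol section 8.0, under the heading on prognostic factors in patients age 65 and older, sets the basis for Table 2: "Based on an 80% power with an assumption of a 25% 100 day mortality in the most favorable group and a delta as indicated". The response is described as "a binary response of alive or dead at 100 days". The table is titled "Number of patients required to test differences in 100 day mortality with 80% power for specified prognostic factors". Five factors (Age, HCT-CI, secondary MDS, cytogenetics, IPSS) then appear under the common column heading "Number of Patients based on expected difference" for delta 0.10, 0.15 and 0.20. The first Age line reads "<70 580 246 130"; with 183, 78 and 41 patients aged 70 or over, the Age totals are 763, 324 and 171.

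No test, alpha or continuity correction is given for the table. On the analysis itself the section says: "The final analysis of these factors will be performed in a logistic regression model for 100 day survival". On the target it says "we anticipate that 700 patients will be required to complete an analysis of prognostic factors for early outcome in patients 65 and older". The factor distributions and the Table 2 power calculations are to be looked at again after 500 patients, when "Adjustments will be made to the final accrual projections at that time".

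**The concern.** The printed rows do not behave like the output of one calculation. With everything else equal, a factor whose smaller group holds 24% of patients (Age, 183/763) should need fewer patients than one whose smaller group holds 20% (secondary MDS, 163/812). That is so at delta 0.10 (763 against 812) and 0.15 (324 against 332), but at delta 0.20 the order reverses (171 against 167).

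If the rows come from different methods, or from rates other than those stated, 80% power means different things in different rows. Readers could not rank the factors by feasibility, and the 500-patient review would adjust accrual from figures that are not comparable.

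**Working it through.** **Inputs.** Power 80%, a 25% reference rate and the three deltas come from section 8.0. Group shares come from each factor's printed delta 0.10 column. Two-sided 5% is inferred because it reproduces the table.

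**Formula.** With p1 in the larger group, p2 in the smaller, k = smaller/larger and p̄ = (p1 + k·p2)/(1 + k), the larger-group size is

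n = [1.960·√((1 + 1/k)·p̄(1 − p̄)) + 0.842·√(p1(1 − p1) + p2(1 − p2)/k)]² / delta².

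The continuity-corrected size is n′ = (n/4)·[1 + √(1 + 2(1 + k)/(n·k·delta))]². Totals are n(1 + k) or n′(1 + k).

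**Reproducing Age at delta 0.10.** k = 183/580 = 0.3155, p1 = 0.25, p2 = 0.15, p̄ = 0.2260.
- Uncorrected: n = (1.674 + 0.647)²/0.01 = 538.8; total 708.8, about 709.
- Corrected: n′ = (538.8/4)·(1 + √1.1548)² = 579.7; total 762.7, which is the printed 580 + 183 = 763.

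**All rows at 25% against 25% minus delta** (totals at delta 0.10 / 0.15 / 0.20):

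| Factor | Printed | Uncorrected | Corrected |
|---|---|---|---|
| Age | 763 / 324 / 171 | 709 / 288 / 145 | 763 / 324 / 171 |
| HCT-CI | 516 / 207 / 104 | 515 / 207 / 102 | 555 / 233 / 122 |
| Secondary MDS | 812 / 332 / 167 | 809 / 329 / 165 | 870 / 370 / 195 |
| Cytogenetics, before unknowns | 570 / 231 / 116 | 569 / 230 / 115 | 613 / 259 / 136 |
| IPSS, sum of groups | 525 / 212 / 105 | 524 / 211 / 105 | 565 / 238 / 125 |

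Age matches the corrected column in all three cells. The other four factors match the uncorrected column within three patients in all twelve. Under either single method Age needs fewer patients than secondary MDS at every delta, so the reversal at 0.20 comes from mixing the two.

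Other conventions were tried. Putting 25% in the smaller group and 25% minus delta in the larger comes near some cells (HCT-CI uncorrected 506 / 201 / 97), but gives Age 657 / 252 / 115 uncorrected or 711 / 286 / 141 corrected. A one-sided 5% test at 25% against 25% plus delta gives larger Age groups of 530 / 242 / 140 uncorrected or 571 / 269 / 161 corrected, against the printed 580 / 246 / 130.

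**Power of the printed numbers.** Power = Φ{[delta − 1.960·√(p̄(1 − p̄)(1/nL + 1/nS))] / √(p1(1 − p1)/nL + p2(1 − p2)/nS)}, where nL and nS are the two group sizes. For Age at 580 + 183: Φ{(0.1 − 0.0695)/0.0319} = Φ(0.955) = 83.0%. The other two columns give 85.1% and 87.7%. If the corrected test was meant, the other four factors have about 77%, 74% and 70–72%.

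**At the stated rates (25% against 25% plus delta, smaller group worse).** For Age at delta 0.10, p2 = 0.35 and p̄ = 0.2740, so n = (1.785 + 0.802)²/0.01 = 669.3 and the total is 880.5, about 881. Across the deltas Age needs about 881 / 404 / 233 uncorrected and 935 / 440 / 259 corrected. The printed 763 gives 74.3% power. At delta 0.10, uncorrected, HCT-CI needs about 666, secondary MDS 997, cytogenetics 722 before unknowns, and IPSS 675. No row of the table is reproduced at these rates.

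**Age at 700 patients.** At delta 0.10, power is 79.5% uncorrected or 76.0% corrected for 25% against 15%, and 70.8% uncorrected for 25% against 35%. At delta 0.15 it is 99.6% or 95.5% (uncorrected, lower and higher rates respectively).

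**Addition.** IPSS at delta 0.15: 125 + 87 = 212, printed as 202.

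**The case against.** A reader might infer that the Age requirement is simply overstated and should be cut to about 709/288/145. The documents do not support that. Those figures are lower only relative to the other rows, and only at rates that contradict the stated assumption. At the stated rates 763/324/171 is already too small, and cutting it would widen the gap (709 against about 881 at delta 0.10).

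A reader might also argue that logistic regression carries no continuity correction, so Age must be the faulty row. Section 8.0 names the model but no test statistic, and the choice matters. By exact enumeration at 25% against 5%, counting samples with a zero cell as non-rejections, a Wald logistic test has about 73% power at the printed 130 + 41 and about 60% at 110 + 35. An uncorrected chi-square test has about 83% at 110 + 35. At delta 0.10 and 0.15 the uncorrected sizes give about 80% with either test. So the plan does not settle which row is out of line.

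The strongest defence is that nothing turns on this. No row equals 700, Age exceeds 700 at delta 0.10 by either formula (763 or 709), secondary MDS exceeds it as well (812), and the projections are to be reviewed at 500 patients. These analyses are also separate from the comparison sized at 240, and alpha and test could sit in an analysis plan. Much of this stands: it limits the consequence, and the missing alpha is not itself the finding. It does not excuse printed figures that disagree with each other and with the sentence introducing them, in the table that the 500-patient review will reopen.

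**Conclusion.** The point holds as an inconsistency, not as a claim that Age is too large. Assuming a two-sided 5% level, Age was sized with a continuity correction and the other four factors without it. Relative to the other rows, Age is inflated by about 8%, 12% and 18% at the three deltas (763/709, 324/288, 171/145). If the correction was intended, it is the other four rows that fall short.

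The larger discrepancy is in the rates. The table reproduces only with the smaller group at a lower mortality than 25%, whereas the text makes 25% the better group's rate. Taken as written, at delta 0.10 Age needs about 15% more than printed (881/763) and the other factors about 23% to 29% more (997/812 to 666/516). Which rates were intended cannot be decided from the document. The 202 is an addition slip and needs no assumption. The practical effect falls mainly on the delta 0.10 column, where Age power at 700 patients ranges from 79.5% to 70.8% (uncorrected) depending on the rates. At delta 0.15, 700 patients suffice for Age either way.

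**What to change.** Recompute every row of Table 2 with one test and alpha, named under the table, at rates that agree with the stated assumption. If the lower rates were intended, correct the sentence instead and keep those rates. Change the IPSS total at delta 0.15 from 202 to 212 if the existing rates are kept. Do not adopt about 709/288/145 as Age targets unless 25% against 25% minus delta is confirmed and the named test carries no correction. If a Wald test is chosen, check the delta 0.20 column by simulation or enumeration.

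Then state the power that 700 patients give for each factor and use the corrected table at the 500-patient review. The cost is one table recalculation and a short wording change, with no new data. The restated requirements may be less favourable, and any accrual consequence can be taken up at the review already planned.
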